They will have multiple opportunities to ask any questions that they may have, and they will also be provided with the clinic's contact information to get in touch with research investigators to address any additional questions or concerns.

Subjects will be reassured that participation is completely voluntary and does not affect their treatment, their relationship with their providers, or the university to minimize the possibility of coercion or undue influence. The patients will be asked that they understand the opportunity to participate and their complete freedom to decline. This will also be asked if they understand and if they have any questions. There is no minimum time period needed between informing the patient of the study and time of consent. Subject will be encouraged to take as much time as they need.

This study will obtain HIPAA authorization prior to enrollment. HIPAA authorization is embedded within the study consent form, which will be reviewed with all participants by the physician or research coordinator obtaining consent. Specific information that will be obtained includes prior medical history, surgical history, reproductive health history including child bearing, drug allergies, age, and ethnicity. This information will be obtained by health care providers, not research coordinators, as deemed necessary for a

Randomized trial on expectations and pain control advancement in surgery: REPAIR

more complete and accurate medical history of the patient and is part of the standard of care during preoperative assessment.

Spanish speaking patients will be included. We will submit the translated documents once the study is approved by the IRB.

Cognitively Impaired Adults will not be included in the study.

All subjects will be 18 years of age or older. No infants, children or teenagers will be enrolled in the study.

26. Documentation of Consent

We plan to document consent, and the Consent form is attached. We do not plan on collecting/storing tissue samples. We will have the option to consent verbally. We will not be using a script, information sheet, or other mechanism.

27. Study Test Results/Incidental Findings

We do not intend to share study test or procedure results with study participants. Additionally, we do not anticipate that the research being conducted will result in incidental findings. Every patient will receive the practice's standard of care regarding a pre-operative work up, which may include different laboratory tests and imaging studies, as determined by their other active medical issues. These results are not part of the research being conducted and will hence be disclosed to the patient as appropriate for standard of care.

28. Sharing Study Progress or Results with Subjects

The patients will not be masked to their study arm. We do not intend to seek out study participants to disseminate information once the study is complete. Women who are interested in the results will be provided the information where to read the manuscript once it is published. Study results for individual participants will not be shared.

29. Inclusion of Vulnerable Populations

There will not be any vulnerable populations included in this study. Those electing for surgery will not be coerced into doing so, nor will they be coerced into participating in this trial.

30. Community-Based Participatory Research

NA. There will be no involvement of the community in this research.

31. Research Involving American Indian/Native Populations

NA. This research does not specifically target this population. If a Native American woman is a candidate for this study, she will be offered participation.

32. Transnational Research

NA. This study is not transnational.

33. Drugs or Devices

NA. This research does not involve drugs or devices.

Checklist Section

This section contains checklists to provide information on a variety of topics that require special determinations by the IRB. Please complete all checklists relevant to your research.

I. Waivers or Alterations of Consent, Assent, and HIPAA Authorization

A. Partial Waiver of Consent for Screening/Recruitment

We are not requesting a partial waiver of consent

Partial Waiver of HIPAA Authorization for Screening/Recruitment

We are requesting a partial waiver of HIPAA authorization to prescreen participants. Investigators will review the medical records of potential participants in PowerChart to determine if they are a good candidate for participation. They may review information such as medical history including surgeries and medications.

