Outcome Measures

Primary Outcome: *1. Opioid Consumption* -- Opioid consumption determined by pill counts and translated into Morphine Milligram Equivalents (MMEs), within 2 weeks of hospital discharge. Patients will be required to bring their narcotic medications for pill counts at their routine 2-week follow-up appointment, since this is the most reliable method for checking opioid use. A medication diary will document pattern of opioid and non-narcotic use and may potentially serve as a behavioral modification tool for narcotic consumption.

Important Secondary Outcomes: *1. Opioids prescribed at hospital discharge and Opioids consumption at 6-week follow-up. 2. Patient Reported Outcomes Measurement*

Information Systems (PROMIS)²⁹ Physical Function SF & Pain Interference Questionnaires -- at baseline, 2 and 6 week follow-up. These validated questionnaires (available in English and Spanish) measure patient-reported physical activity and pain in the preceding 7 days.³⁰ Raw scores are translated into standardized scores; mean T-score represents the average score of the general population and a difference of 10 points represents 1 SD away from the mean.

Other Secondary Outcomes: *Patient Satisfaction and Preparedness for Surgery:* We will administer Global Questionnaires assessing (1) satisfaction with pre-operative education and care and (2) assessing patient's perceptions regarding preparedness for surgery.

These will be administered to both Spanish and English speaking patients. Questionnaires will be scored on a 1-5 Likert scale (Strongly disagree to Strongly agree). (Other validated post-operative satisfaction and preparedness questionnaires are not readily available in Spanish; existing Spanish questionnaires are condition-specific -- general or urogynecologic post-operative questionnaires are not currently validated.)

4. Inclusion and Exclusion Criteria

We will recruit women cared for by the University of New Mexico Urogynecology practice at UNMH Women's Care Clinic or Sandoval Regional Medical Center undergoing pelvic floor surgery. Patients who have elected to proceed will be offered study enrollment if they meet the inclusion and do not meet the exclusion criteria.

The *inclusion criteria* are:

1. Subjects are \geq 18 years of age
2. English or Spanish speaking
3. Patient scheduled for pelvic floor surgery

Exclusion criteria are as follows:

1. Unable to speak English or Spanish

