2. Using long acting opioids (e.g. MS Contin, Fentanyl patch)
3. Primary or Pain Healthcare Provider recommends against study participation (eg. If the patient has a history of opioid use disorder or other confounding problems, we will contact the Primary Care Provider or Pain Healthcare Provider for their recommendations regarding study participation)
4. Undergoing surgeries that involve: Neuro/Interstim, Cysto/hyrdro distension, vaginal botox, mesh excision/complications

Special populations such as adults unable to consent, individuals who are not yet adults, pregnant women, and prisoners will not be included in this study.

We will be excluding women who are unable to speak and understand either English or Spanish. The justification for this is the satisfaction surveys are only available in English and Spanish and include the majority of the patients care by our group. Because these are our secondary objectives, it is important to use these standardized surveys. Additionally, we can only conduct focus groups in English or Spanish given our qualitative team is bilingual only in English and Spanish.

5. Number of Subjects

This a qualitative and randomized control trial at a single site – the University of New Mexico's Urogynecology department.

Up to 60 participants will be recruited for the focus groups and up to 198 people will be recruited for the randomized controlled trial at UNM.

Power Calculation & Statistical Analysis:

Based on our prior qualitative experience; approximately 10-12 participants must be recruited to have 6-8 attend the focus group. We plan to conduct 4 focus groups; and need to recruit 48 subjects. Given it is possible thematic saturation will not be achieved after 4 focus groups; we will recruit additional subjects and complete additional focus group until saturation is obtained. Although a few studies describe

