opioid prescribing practices following Ob-Gyn surgery, we could not find any studies that reported opioid *consumption* following gynecologic or urogynecologic surgery. In order to perform the power calculations necessary for Specific Aim 2 (comparing opioid use between groups), because the actual number of opioids consumed following urogynecologic surgery is unknown, we will assume that patient-centered pre-operative education will result in a 33% decrease in narcotic consumption following hospital discharge compared to the control group. If we assume that controls consume a mean of fifteen 5 mg oxycodone pills (SD of +/-11 pills), and if we assume that the patient-centered group consumes 33% fewer pills (i.e. 10 pills in the modified education group), we would need a total of 152 participants (76 per group) to complete treatment and follow-up for a two-tailed t-test to have 80% power at $\alpha=0.05$. Assuming approximately 30% of patients will cancel surgery after randomization (including medical or insurance issues or change their mind) or will be lost to follow-up; we would need to enroll up to 198 women (99 per group) or until our designated power is met. We will perform between group comparisons using Chi-squared tests for categorical variables and t-tests for continuous variables. We anticipate that specific covariates (e.g. baseline questionnaire results, and narcotic use in last 3 months) may be confounders and that multivariable analyses will be required to evaluate the between group differences in outcomes. Note 1: When studies involve consent, an individual is considered a research subject once they have provided consent. If the research includes screening procedures after consent, please indicate the number of subjects that need to be recruited and the number that will actually participate in the research post-screening.

6. Study Timeline

Subjects in Aim 1 will participate in one focus group. Subjects in Aim 2 will participate up to the 6 week post-operative visit. This could occur within a window up of up to 8 weeks past their surgery.

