All surgeries will take place at UNM Main, OSIS or SRMC operating rooms. Questionnaires and data collection will occur in the Urogynecology clinics at UNM or SRMC, by phone, HIPAA compliant Zoom or email link to REDCap, whichever is best for the participant. All data will be collected prospectively.

Participant Flow through the Study: Figure 1 (N range pending funding)

Randomized trial on expectations and pain control advancement in surgery: REPAIR

13. Data Analysis

Power Calculation & Statistical Analysis: Although few studies describe opioid prescribing practices following Ob-Gyn surgery, we could not find any studies that reported opioid *consumption* following gynecologic or urogynecologic surgery. In order to perform the power calculations necessary for Specific Aim 2 (comparing opioid use between groups), because the actual number of opioids consumed following urogynecologic surgery is unknown, we will assume that patient-centered pre-operative education will result in a 33% decrease in narcotic consumption compared to the control group. If we assume that controls consume a mean of fifteen 5 mg oxycodone pills (SD of +/-11 pills), and if we assume that the patient-centered group consumes 33% fewer pills (i.e. 10 pills in the modified education group), we would need a total of 152 participants (76 per group) to complete treatment and follow-up. Assuming approximately 30% of patients will cancel surgery after randomization or will be lost to follow-up; we would need to enroll 198 women (99 per group). We will perform between group comparisons using Chi-squared tests for categorical variables and t-tests for continuous variables. We anticipate that specific covariates (e.g. baseline questionnaire results, and narcotic use in last 3 months) may be confounders and that multivariable analyses will be required to evaluate the between group differences in outcomes.

14. Provisions to Monitor the Data to Ensure the Safety of Subjects

Subjects will participate in focus groups and then receive preoperative education and shared decision making on quantity of opioid prescribed postoperatively. Therefore the risks inherent to participation in the study are only minimal. As this is a minimal risk study, our Data Safety Monitoring Plan will entail the review of data monthly by staff and the PI or a mentoring co-investigator. We will assess for harm such as over treatment

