of pain, which is highly unlikely as we are complying with our standard of care. It would be unlikely that the study would require suspension as patients in the intervention arm are actually having less exposure to harm than the standard of care arm. Specific findings we will be looking for are adverse events, serious adverse events and reportable new information.

15. Withdrawal of Subjects

Any participant may withdraw from the study at any time without penalty and will continue to receive the clinical standard of care. A subject may be withdrawn from the study without her consent at the discretion of the physician and study staff if they believe she no longer meets study inclusion criteria or if she meets exclusion criteria, or if they believe that it is not in her best interest to continue study participation. Investigators may withdraw a subject if the subject is not following the study protocol. If a woman is withdrawn from the study either at her own discretion or that of the research staff, she may continue with the planned surgical procedure performed in the usual fashion.

To minimize withdrawal from the study, patients will be randomized at their pre-operative visit. According to the 2010 CONSORT guidelines, we will analyze all participants assessed for eligibility within the study. We will document reasons for withdrawal from the study including failure to meet eligibility criteria or participant declining enrollment into the study. We will report eligibility criteria not met or reasons for declining participation in the study. The withdrawal procedure is clearly documented in the study consent.

16. Data Management/Confidentiality

Randomization assignment will be generated by a computer based randomization table and assigned by a research coordinator. Assignments will be kept in sealed opaque envelopes numbered sequentially, and on the day of the patient's pre-operative visit, the surgeon will call a research coordinator who will open the next envelope in the sequence. All data collection sheets and questionnaires will contain the subject number and day of the clinic visit or day of completion. No other patient identifiers will be collected. PHI including patient name, date of birth, phone number, and medical record number will need to be collected to track for appointments.

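### Type of operation and clinic are used neither in the allocation nor as named covariates, although both are known at the pre-operative visit; the cost is precision and credibility, not bias

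*Combined protocol and SAP*

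**What the plan says.** **Allocation.** Section 16 states: "Randomization assignment will be generated by a computer based randomization table and assigned by a research coordinator". The envelopes are opaque, sealed and numbered in order. On the day of the pre-operative visit the surgeon calls a coordinator "who will open the next envelope in the sequence". No strata, blocks or minimisation factors are mentioned. The word unstratified does not appear, but a single sequence is the natural reading.

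**Case mix.** The inclusion criterion in section 4 is broad: "Patient scheduled for pelvic floor surgery". One exclusion narrows it: "Undergoing surgeries that involve: Neuro/Interstim, Cysto/hyrdro distension, vaginal botox, mesh excision/complications".

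**Locations.** Section 12 states: "All surgeries will take place at UNM Main, OSIS or SRMC operating rooms". Patients are seen at two clinics, UNM and SRMC, run by one division.

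**Analysis.** Sections 5 and 13 plan t-tests for continuous outcomes and expect that multivariable analysis will be needed. The covariates given as examples are baseline questionnaire scores and recent narcotic use. Neither operation nor clinic is mentioned.

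**Sample size.** Both sections assume that "controls consume a mean of fifteen 5 mg oxycodone pills (SD of +/-11 pills") against "10 pills in the modified education group", and conclude: "we would need a total of 152 participants (76 per group) to complete treatment and follow-up".

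**The concern.** Opioid use after discharge plausibly depends on how extensive the operation is. Women are eligible only once surgery is scheduled, and they are allocated at the pre-operative visit, so the planned operation is known in time to be used. As written, it enters neither the allocation nor the stated primary comparison.

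Two things are at stake. The first is precision: variation between operations stays in the error term when it could be removed. The second is credibility: the covariate list is given only by example. If the arms visibly differ in case mix, the team would have to choose a model after seeing the data. An adjusted and an unadjusted result could then disagree, with nothing in the plan to say which is primary.

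**Working it through.** **Inputs from the documents** (sections 5 and 13): control mean 15 pills, SD 11, planned difference 15 − 10 = 5 pills, 76 completers per arm, two-sided α 0.05, power 80%. The primary outcome is in MMEs and the sample size is in 5 mg pills. Expressed as shares of the planned effect, the results do not depend on the unit.

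**Inputs assumed:** two operation classes, half the women in each, and a gap in mean consumption between classes of 3, 5, 8 or 10 pills. The documents give neither the case mix nor consumption by operation, and they call overall consumption unknown.

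**Step 1. The plan's own figure.** n per arm = 2 × (1.960 + 0.842)² × 11² / 5² = 76 by the normal approximation, which matches the plan. The exact t-test needs 77 per arm and has 79.5% power at 76.

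**Step 2. Size of a chance imbalance.** The SD of the between-arm difference in class share is √(2 × 0.5 × 0.5 / 76) = 0.081, or 8.1 percentage points. The 95% limit is 1.96 × 8.1 = 15.9 points.

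**Step 3. Shift in the primary difference** = gap × imbalance, as a share of 5 pills.

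**Step 4. Gain from accounting for class.** Share of variance explained R² = 0.25 × gap² / 121; residual SD = 11 × √(1 − R²); t-test power recomputed at 76 per arm.

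| Gap (pills) | Shift at 1 SD | Shift at 95% limit | R² | Residual SD | Power |
|---|---|---|---|---|---|
| 3 | 0.24 (5%) | 0.48 (10%) | 2% | 10.90 | 80.2% |
| 5 | 0.41 (8%) | 0.79 (16%) | 5% | 10.71 | 81.6% |
| 8 | 0.65 (13%) | 1.27 (25%) | 13% | 10.25 | 84.8% |
| 10 | 0.81 (16%) | 1.59 (32%) | 21% | 9.80 | 87.8% |

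With a 30/70 mix the 95%-limit shifts for these gaps are 9%, 15%, 23% and 29%.

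**Step 5. Validity of the planned t-test.** The standard error of the difference is 11 × √(2/76) = 1.78 pills. If the SD of 11 describes the whole eligible mix, the shifts above are already part of that error. In 40,000 simulated trials at each gap of 0, 5 and 10 pills, with total SD held at 11, type I error was 4.8% to 5.1% and power 79.4% to 79.5%.

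**Step 6. Is adjustment without stratification enough?** With a 50/50 mix and equal arms, the correlation between arm and class equals the imbalance. At the 95% limit, adjustment therefore inflates the variance by 1 / (1 − 0.159²) = 1.026, or under 3%. Adjustment alone recovers most of the gain.

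**The case against.** Simple randomisation is legitimate at this size, and the stated test keeps its error rate and its planned power. The multivariable analysis is already foreseen and its covariates are only examples, so operation type is not ruled out. The four excluded procedure groups narrow the mix, and the feasibility count in section 6 refers to major operations. A manual of operations is also planned and could hold detail on how the list is built.

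Much of this stands. It means the gap is an incompletely specified analysis more than a faulty allocation. It does not remove the point, because a covariate that is merely allowed is not prespecified, and the feasibility count is not an eligibility limit.

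A reader might draw stronger conclusions that the documents do not support:

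- **That imbalance could move the result by a third of the planned effect.** At the 95% limit with a 50/50 mix this needs a gap of about 10.5 pills, roughly two thirds of the assumed control mean. The chance of a shift that large is 4.0% at a 10-pill gap and 0.004% at a 5-pill gap.
- **That the comparison is biased or the test invalid.** Step 5 shows otherwise.
- **That prescribing differs between hospitals, or that case mix drifted apart between arms over the pandemic halt.** One division runs both clinics, nothing in the documents measures either effect, and the absence of blocking is inferred only from silence.

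**Conclusion.** The plan neither stratifies on operation or clinic nor names them for adjustment. The consequence is a forgone gain in precision and an avoidable argument over interpretation. At 76 per arm and a 50/50 mix, a 95%-limit imbalance would shift the primary difference by about 10% to 32% of the planned 5 pills for gaps of 3 to 10 pills, and a 1-SD imbalance by about 5% to 16%. Accounting for operation class would lift power from about 79.5% to about 82% to 88% for gaps of 5 to 10 pills, but only to about 80% for a 3-pill gap.

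These figures rest on assumed gaps and an assumed mix. No size can be given for clinic. The participant-flow figure was not readable in the text available, so a statement about stratification there cannot be excluded.

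**What to change.** **Main change, sections 5 and 13.** Before any comparison by arm, prespecify the primary comparison of 2-week MMEs as a linear model adjusted for planned operation class and clinic (UNM or SRMC), in place of the unadjusted t-test. Fix the two operation classes in advance, for example in the manual of operations, and analyse each woman in her planned class. State at the same time which of the covariates now given as examples belong in the primary model.

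**Secondary change, section 16.** The timeline in section 6 and the account of telephone consent in section 25 suggest that recruitment is already under way, so a new list cannot balance women already allocated. For those not yet allocated, use permuted blocks of randomly varying size, stratified by planned operation class, and by clinic if practicable. Both factors together give four strata.

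**Cost.** Two model terms, a regenerated list and separate envelope sets. The planned operation must be recorded before allocation, and a few women will have a different operation from the one planned. Blocking makes the next assignment slightly more predictable in a trial where patients are unmasked and the surgeon calls for the allocation; varying block sizes limit this. Clinic does not distinguish all three operating locations, so OSIS is not separately represented.
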